Protocol Title: Prospective Randomized Control Trial of Open versus Robotic REtrOmuscular Ventral Hernia repair [ORREO Trial]

NCT: 03007758

Date: 07 Apr 2017

ORREO Trial Protocol:

Date: 07Apr2017

Title: Prospective Randomized Control Trial of Open versus Robotic REtrOmuscular Ventral Hernia repair [ORREO Trial]

PI: [name]

Co-I: [name], DO
[name], APRN, NP-C

Background:

Due to the variety of hernia repair techniques and materials available, and the heterogeneity of the hernia patient population, there is no consensus standard of care for ventral hernia repair. The Rives-Stoppa retromuscular hernia repair is considered by many the standard by which all other techniques should be compared {Israelsson:2006gn}{Helgstrand:2013ev}. There is good long term data on this technique, with overall recurrence rate of 7.4% and wound complication rates of 9.3% (3). Unfortunately, many factors that lead to development of ventral and incisional hernias are also those that increase the risk of recurrence and wound morbidity. Obesity, COPD, DM, and tobacco abuse are particularly troublesome conditions that confer higher morbidity after abdominal wall reconstruction (AWR). While preoperative weight loss and smoking cessation are modifiable risk factors, many patients will not successfully lose weight, are not eligible for bariatric surgery, will not stop smoking, and are at risk for developing increasingly complex hernias or presenting with acute incarceration requiring urgent repair.

Since its initial description, laparoscopic ventral hernia repair (LVHR) was quickly adopted and has been shown to significantly decrease wound morbidity, with comparable recurrence rates (2) (3) (4). Though our preferred technique is an open retromuscular VHR (OVHR), laparoscopy remains an important technique for high risk patients. However, the hernia defect itself is typically not closed, which can result in pseudorecurrence and eventration of the mesh through the hernia defect, particularly with larger defects (5). Additionally, mesh placed in the intraperitoneal position has the potential to complicate subsequent abdominal operations, with incidence of unplanned enterotomy or bowel resection as high as 20% (6) (7).

The development of our robotic retromuscular ventral hernia repair (RRVHR) technique combines the benefits of the OVHR (reconstruction of native anatomy and a functional abdominal wall, placement of mesh in the retromuscular space) with those of LVHR (lower wound morbidity). Understandably, during the early development of a novel technique, we have been highly selective of our patients, typically selecting those we deem to have a high chance of a successful repair, and those with small to moderate defects as we refined the technical details of the operation. As our experience has increased and technique refined, we have been able to repair more complex patients with larger, more complex hernia defects. We

anticipate that these patients with the highest risk of wound morbidity will have the greatest clinical benefit from the robotic approach.

We describe a novel surgical technique, using new technology to duplicate the abdominal wall reconstruction achieved with OVHR in a minimally invasive fashion. While the feasibility of robotic VHR has been described, previous reports describe essentially a LVHR with intraperitoneal mesh placement utilizing the robot rather than a laparoscope. The only other report of a similar technique, and the inspiration of our development of RRVHR, is a transabdominal, retromuscular repair of umbilical hernia with plication of diastasis rectus described by [name] (8). The ability to duplicate a complete abdominal wall reconstruction with mesh reinforcement in high risk patients using a minimally invasive technique is a significant step forward in improving the outcomes in VHR. To our knowledge, we have the largest experience with this technique and the first reported outcomes data, which were presented at the World Hernia Congress, April 2015 (10).

Purpose:

The purpose of this study is to determine how the robotic retromuscular hernia repair compares to the open retromuscular hernia repair for large hernia defects in patients at higher risk of wound complications.

Hypothesis:

We hypothesize that the robotic retromuscular ventral hernia repair improves the clinical composite outcome, as compared to open retromuscular hernia repair, in high risk patients.

Primary Endpoints:

1. Composite Outcome (See full description below)
 - a. Surgical Site Occurrence (excluding simple seroma)
 - b. Surgical Site Infection
 - c. Hospital Readmission
 - d. Hernia Recurrence

Secondary Endpoints:

1. All Surgical Site Occurrences
2. Surgical Site Occurrences requiring procedural intervention
3. All Surgical Site Infections
4. Surgical Site Infections requiring procedural intervention
5. Length of Stay
6. Operative Time
7. Quality of Life
8. Cost

Composite Outcome:

In order to adequately power this study and provide a clinically relevant outcome measure, a composite outcome was designed to capture the outcomes that are considered clinically

significant. As such, simple seroma, which is very common, is excluded. Any seroma requiring procedural intervention will be included. Management of seroma or hematoma requiring intervention is discussed below under “Management of Complications.” Other SSOs, such as skin dehiscence, cellulitis, hematoma or skin necrosis, are included as these are more likely to require some intervention, such as local wound care or drainage, or some additional cost, such as antibiotic therapy. Similarly, SSIs frequently require additional intervention and cost.

Study Design:

Prospective randomized control trial of robotic retromuscular ventral hernia repair versus open retromuscular ventral hernia repair in patients at high risk for adverse outcome. [Open versus Robotic REtrOmuscular Incisional hernia repair; ORREO trial]

Patient Selection:

All patients presenting to the Greenville Health System Hernia Center who meet the inclusion criteria will be considered for enrollment. Patients who agree to participate will be randomized to robotic retromuscular ventral hernia repair (group 1, RRVHR) or open retromuscular ventral hernia repair (group 2, OVHR). Randomization will occur in the office setting to allow appropriate scheduling of the case.

Participant Enrollment: 50 patients per study group (100 patients total)

Inclusion Criteria:

>18 years old

Ventral or incisional hernia measuring $\geq 7\text{cm}$ and $\leq 15\text{cm}$

At least one of the following risk factors:

BMI >30

COPD

DM

Current smoker (within 1 month)

Exclusion Criteria:

Current abdominal or abdominal wall infection

Presence of ileostomy, colostomy, or ileal conduit

CDC wound class 3 or 4

Hernia defect $< 7\text{cm}$ or $>15\text{cm}$

Pregnant women will be excluded from participating in this study.

Methods:

Prospective randomized control trial of robotic retromuscular ventral hernia repair versus open retromuscular ventral hernia repair in patients at high risk for adverse outcome. [Open versus Robotic REtrOmuscular Incisional hernia repair; ORREO trial]. Patients who agree to participate will be randomized to robotic retromuscular ventral hernia repair (group 1, RRVHR) or open retromuscular ventral hernia repair (group 2, OVHR). Randomization will be performed using the randomize function in the Redcap database.

Data Collection:

All patients will be entered prospectively into the Americas Hernia Society Quality Collaborative (AHSQC) database and followed prospectively. For data points that will be collected for trial purposes that are not contained within the AHSQC dataset, a Redcap database will be used.

Within the AHSQC, the following data is collected: Preoperative Patient Reported Outcomes via a validated, hernia specific quality of life questionnaire. Demographic data include age, sex, ethnicity, zip code, and insurance coverage. Patient characteristics include DM, COPD, HTN, immunosuppression, smoking status, hepatic disease, renal disease, antiplatelet or anticoagulant therapy, height/weight/BMI, history of previous hernia repair (including number of repairs, type of repair, type of mesh), history of previous abdominal wall infection, and functional status. Operative details include hernia width, height, presence of prior mesh, operative time, mesh selection, size of mesh placed, position of mesh placement, choice of mesh fixation, ability to close the midline fascia, technique for closure, use of component separation technique, and intraoperative complications. Hospital data will include LOS and any acute medical complications. Postoperative follow-up will occur at 2 weeks, 6 weeks, 6 months, 1 year, and 2 years. Patient Reported Outcomes will be collected at each of these post-operative visits. Cost data will be obtained from the Greenville Health System office of Business Intelligence after discharge from the index hospital stay, and include any readmission or additional procedural intervention.

Additional data not contained within the AHSQC, including patient account number, total operative time in minutes, total anesthesia time, and EBL, will be collected prospectively and recorded at the time of surgery completion. Operative time will be recorded as total anesthesia time and total operative time.

Operative Technique**Open Retromuscular Technique**

- Midline laparotomy
- Adhesiolysis
- Removal of any prior mesh
- Defect measurement
- Bilateral retromuscular dissection, extending at least 5cm above and below the defect
- TAR (if necessary for posterior / anterior fascial closure OR for mesh coverage of more laterally oriented defect)
- Posterior sheath closure
- Dissected space measured
- Mesh placement (Vitamesh)
- Mesh fixation at minimum of 4 fixation points
- Anterior fascia closure using running, small-bite technique using slowly absorbable suture

- Skin closure with subcuticular fast-absorbing suture and surgical glue
- No drains will be placed

Robotic Retromuscular Ventral Hernia Repair

One of the following techniques, depending on location and technical feasibility.

Double-Dock Technique

- Three right (or left) lateral abdominal wall trocars
- Adhesiolysis and hernia reduction
- Removal of any prior intraperitoneal mesh
- Contralateral retromuscular dissection, extending 5cm above and below defect
- Contralateral transversus abdominis release with placement of right-sided trocars
- Mesh placement (Vitamesh)
- Intracorporeal measurement of hernia defect and dissected space
- Mesh fixation at minimum of 4 fixation points
- Redock on the left (or right)
- Contralateral retromuscular dissection and transversus abdominis release
- Closure of posterior rectus sheath using slowly absorbable self-fixating suture
- Deployment of mesh
- Closure of hernia defect using slowly absorbable self-fixating suture

Single-Dock Technique

- Three right (or left) lateral abdominal wall trocars, with 4th assistant trocar placed, location at the discretion of the surgeon.
- Adhesiolysis and hernia reduction
- Removal of any prior intraperitoneal mesh
- Incision of ipsilateral posterior rectus sheath
- Retromuscular dissection from lateral to medial, ending at the linea alba
- Preperitoneal dissection along the midline, including reduction of the hernia sac
- Contralateral retromuscular dissection
- Contralateral transversus abdominis release (if indicated)
- Intracorporeal measurement of hernia defect
- Closure of hernia defect with slowly absorbable self-fixating suture
- Measurement of dissected space
- Placement of mesh (Vitamesh)
- Mesh fixation at minimum of 4 points

- Closure of posterior rectus sheath

Single-Dock Technique, Epigastric or Suprapubic Dock

- Three trocars along the upper or lower abdomen, with assistant trocar placed at surgeons discretion
- Adhesiolysis and hernia reduction
- Removal of any prior intraperitoneal mesh
- Transverse incision of bilateral posterior rectus sheath
- Bilateral retromuscular dissection, combined with midline preperitoneal dissection extending from at least 5cm below the defect to at least 5cm above
- Unilateral or bilateral transversus abdominis release (if indicated)
- Intracorporeal measurement of hernia defect
- Closure of hernia defect with slowly absorbable self-fixating suture
- Measurement of dissected space
- Placement of mesh (Vitamesh)
- Mesh fixation at a minimum of 4 points
- Closure of posterior rectus sheath

Perioperative Care

- Enhanced Recovery After Surgery (ERAS) protocol will be used for all patients as follows:
 - Preoperative electrolyte beverage 2-4 hours preop
 - Preoperative pain cocktail: (except in case of allergy or other specific contraindication)
 - Celebrex 400mg
 - Lyrica 75mg
 - Tylenol 1000mg
 - Avoidance of intraoperative narcotics
 - Ketamine bolus and infusion intraoperatively
 - Lidocaine infusion intraoperatively
 - Postoperative ketamine infusion continued on floor. Management of ketamine infusion by Anesthesia pain service
 - Postoperative intravenous acetaminophen and ketorolac (except in case of allergy or specific contraindication)
 - Oral narcotic (hydrocodone or oxycodone) given for breakthrough pain only
 - Oral intake beginning not later than morning of postoperative day 1

Management of Complications

- Surgical site infections will be managed by bedside or in-office opening and drainage of the surgical site, or percutaneous drainage of fluid collections as indicated, according with standard surgical principles.
- Operative intervention will be reserved for patients presenting with sepsis, or after failed non-operative therapy.
- Antibiotics at surgeon discretion.
- Surgical site occurrences (seroma or hematoma) will be treated only if patients have ongoing intractable pain related to the seroma, or there is concern for possible infection. Should intervention be required, simple aspiration, repeated as necessary, is the preferred approach, with percutaneous drain placement reserved for patients with suspected infection, or those requiring multiple reaspirations.

Follow-up:

Two week
6 week
6 month
1 year
2 years

Quality of Life

Will be assess via AHSQC Patient Reported Outcomes Quality of life questionnaire will be administered at preoperative visit and each planned postoperative visit, and will be administered by the Study Coordinator, Principal Investigator or Co-Investigator.

Sample Size & Statistical Analysis

Based on our current RRVHR outcomes and utilizing our entire OVHR database, which is maintained in a prospective fashion, we obtained a composite outcome using the combination of SSO (excluding seromas), SSI, hospital readmission, and hernia recurrence. For OVHR, the incidence of the composite outcome is 52.2% and for RRVHR 24.1%. Using a power of 80% and a significance of 5%, we estimate that 46 patients enrolled in each arm will demonstrate a difference in our primary endpoint. We plan to enroll at least 50 patients in each arm to allow for potential patient withdrawal or failure to maintain follow-up.

Differences in discrete primary and secondary outcomes (SSO, SSI, readmission, recurrence) between the OVHR and RRVHR groups will be analyzed using Chi-squared tests, or Fisher's Exact Test for small sample sizes ($N \leq 6$). Differences in continuous outcomes (length of stay, operative time, and costs) between the OVHR and RRVHR groups will be determined using Students t-test and Mann-Whitney U tests. P-values <0.05 will be considered indicative of statistical significance. All analysis will be completed using R statistical software (R version 3.0.2).

Adverse Events: Defined as any unfavorable or any unintended sign, symptom or disease that is reported by the patient to have occurred, or a worsening of a preexisting condition. Adverse events will be recorded and detailed.

Potential Risks:

The following are possible complications specific to hernia repair, and may occur after either open or robotic repair:

- **Seroma:** A seroma is a collection of watery fluid below the skin that occurs in the space that is separated during surgery or in the space where your hernia was. This occurs in up to 50% of patients. This is almost always treated with observation. If treatment is needed, a small needle or tube may be placed to drain the fluid.
- **Hematoma:** A hematoma is a collection of bloody fluid below the skin that occurs in the space that is separated during surgery or in the space where your hernia was. This may occur in about 10-15% of patients. This is almost always treated with observation. If treatment is needed, a small needle or tube may be placed to drain the fluid.
- **Skin dehiscence:** Dehiscence is a separation of the skin at the site(s) of incision(s). This occurs in less than 5% of cases. Treatment may require a gauze or possibly a vacuum dressing to be placed in the wound until it heals. Healing time will depend on the size of the area of the incision that separates.
- **Skin necrosis:** Poor blood flow to a portion of the skin may cause it to die (necrosis). This occurs in less than 5% of cases. Treatment may be simple observation or may require removal of portions of the dead skin and fatty tissue. A gauze or vacuum dressing may be placed in the wound until it heals. Healing time will depend on the size of the area of skin necrosis.
- **Surgical site infection:** A surgical site infection is one that occurs in the skin or fatty tissue, in between the layers of the abdominal wall that are separated to repair the hernia, or inside the abdomen. This occurs in 5-20% of patients. Treatment may require antibiotics, opening of the incision, or placement of a needle or tube to drain the infection. If the incision is opened, a gauze or vacuum dressing may be placed in the wound until it heals. Healing time will depend on the size of the wound.
- **Mesh infection:** Infection may occur in the space where the mesh is located. This occurs in less than 5% of cases. Most often, this is treated exactly as other surgical site infection. However, if the infection does not go away, removal of the mesh may be needed. This is a rare.
- **Bowel injury:** Because we are working inside your abdomen, there is a risk of injury to your small or large intestine, which occurs in about 1% of cases. If this occurs and is seen at the time of surgery, it is repaired immediately. There is a small chance that a bowel injury could be missed, which may cause you to become seriously ill and likely require additional operation(s) to repair the bowel, prolonged hospital stay, or even result in death.

- Hernia recurrence: there is a 5-10% chance that your hernia will come back.

Any surgery has a risk of some complications, which may include:

- Venous thromboembolism (blood clot): Blood may clot within the vessels of the body, causing swelling of the leg(s). This occurs in about 2% of patients. If the blood clot breaks free from the vessels, they can travel to the vessels in the lungs, which can be fatal. Fatal blood clots are rare events. A blood thinner is needed for treatment. You will be given an injection of a blood thinner prior to the operation, as well as devices that will squeeze your calves, in order to prevent you from getting any blood clots.
- Respiratory complications, such as pneumonia or difficulty breathing. In rare cases, this may require you to be placed on a ventilator, a machine that assists in breathing, for a short period of time.
- Heart complications, such as heart attack, irregular heart rhythm, or heart failure.
- Ileus, which is a slowness of your intestine that may cause nausea or vomiting, may occur in 5-10% of cases. Treatment may require a tube placed through your nose to help empty your stomach.

Some of the questions in the quality of life questionnaire are of a personal nature and may be upsetting to some participants. Participants do not have to answer any questions that they do not want to answer.

This study may involve unknown risks to an unborn or nursing child. Women who are pregnant or nursing child may not participate in this study.

The study records are considered confidential, but absolute confidentiality cannot be guaranteed. This study may result in presentations and publications, but steps will be taken to make sure participants are not identified by name.

Potential Benefits:

It is not possible to know if there will be any potential benefit beyond what is expected for treatment utilizing the standard of care.

Potential Limitations:

Based on our current data, there is a shorter length of stay with robotic hernia repair compared to open, even though the remaining outcome measures (SSO, SSI, recurrence, SSOPI, SSPI, readmission) are similar, which may bias patients against opting into randomization. This may not impact clinical outcomes, but could prolong the enrollment period. Patients may also be biased in favor of, or against, robotic repair based on patients' preconceived notion of either robotic or minimally invasive surgery.

Participant withdrawal: Participants may refuse to participate or choose to withdrawal from the study at any time without fear of being penalized or losing benefits. Participants may be

withdrawn from the study at any time if it is in the study Physician's judgment that withdrawal is in the participant's best interest, if the participant's medical condition changes or if the participant no longer follows the study instructions.

Informed Consent: The formal consent of a participant, using the GHS IRB approved informed consent form template, will be obtained by the study Physician before the participant undergoes any study procedures. The consent form will be signed and personally dated by the participant, a witness and the person who conducted the informed consent discussion. The original signed informed consent form will be retained in the participant's study records. A photocopy of the informed consent form will be scanned into the electronic system at the Vascular Health Alliance office. A photocopy of the signed informed consent form will be given to the participant for their records at the time of consent.

Safety and Reporting: Adverse Events, Serious Adverse Events and Unanticipated Adverse Device Effects will be reported to the GHS IRB according to OHRP policies 18.0 "Reporting of Unanticipated Problems Involving Risks to Subjects or Others and Adverse Events" and 40.0 Appendices "Reportable Event Reporting Requirements - Appendix A."

Protocol Deviations: Protocol Deviations will be reported to the GHS IRB according to OHRP policy 20.0 "Non-compliance with Regulations, IRB Policies, Procedures or Decisions."

Privacy and Confidentiality: All data for this study will be kept confidential.

Costs: This study is not expected to yield any additional costs to participants. Participants will not be compensated to participate in this study.

References:

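### Does the lack of a stated assessment time for the primary composite leave the primary test open, and does it need a plan change?

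*Combined protocol and SAP*

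**What the plan says.** Primary Endpoints lists "Composite Outcome (See full description below") with four components: surgical site occurrence other than simple seroma, surgical site infection, readmission ("c. Hospital Readmission", with no limit on cause or time) and hernia recurrence. The Composite Outcome section opens with its aim ("In order to adequately power this study and provide a clinically relevant outcome measure, a composite outcome was designed to capture the outcomes") and adds what counts: a seroma only if it needs a procedure, a hematoma without that condition. It gives no period.

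Data Collection sets the visits: "Postoperative follow-up will occur at 2 weeks, 6 weeks, 6 months, 1 year, and 2 years". The sentence after it ties only the quality-of-life data to them: "Patient Reported Outcomes will be collected at each of these post-operative visits". Readmission appears there only under cost data, which are to "include any readmission or additional procedural intervention".

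Sample Size & Statistical Analysis gives planning rates of 52.2% (open) and 24.1% (robotic) from the centre's own data, without a follow-up length. It derives 46 per arm and enrols 50. The test sentence reads "Differences in discrete primary and secondary outcomes (SSO, SSI, readmission, recurrence) between the OVHR and RRVHR groups will be analyzed using Chi-squared tests", with Fisher's exact test for small samples, and "P-values <0.05 will be considered indicative of statistical significance". It names no visit.

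Potential Risks describes seroma as watery and hematoma as bloody fluid, and says both are nearly always just observed.

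**The concern.** A chi-squared test needs one yes or no per patient over one period. The components can arise at different times, so the composite at 6 weeks, 1 year and 2 years would be three different endpoints, and a primary analysis at any of them would comply with the text. If the choice followed the data, the 5% level would no longer hold.

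Two related gaps add to this. The stated power carries over to the trial only if 52.2% and 24.1% were counted over a similar follow-up. And an undrained hematoma is a primary event while an undrained simple seroma is not, yet Management of Complications handles both under one rule, and no diagnostic criterion separates them when no fluid is seen. Seroma is put at up to 50% of patients and hematoma at 10-15%, so the label could decide many outcomes.

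**Working it through.** **1. The plan's sample size.** Inputs from Sample Size & Statistical Analysis: p1 = 0.522, p2 = 0.241, 5% two-sided (sidedness assumed), 80% power. The mean rate is (0.522 + 0.241)/2 = 0.3815.

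n = [1.960·√(2·0.3815·0.6185) + 0.8416·√(0.522·0.478 + 0.241·0.759)]² / (0.522 − 0.241)²

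= [1.960·√0.4719 + 0.8416·√0.4324]² / 0.07896 = 3.609/0.07896 = 45.7, so 46 per arm.

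This matches. Enrolling 50 covers a loss of 1 − 46/50 = 8%. Power at 50 per arm is 83.9% by exact enumeration of the chi-squared test (83.5% by the normal approximation).

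**2. One count, one test.** With no true difference, 50 per arm and a common rate of 24.1%, 38% (about the mean of the two planning rates) or 52.2%, the exact false-positive rate is 4.4%, 5.1% or 5.7%. The small-sample rule is read as Fisher's test if any cell is 6 or fewer, otherwise uncorrected chi-squared.

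**3. Free choice among five visits.** The documents give no event timing, so four patterns are assumed for the cumulative share of 2-year events at the five visits. Cumulative counts are followed exactly in both arms, and a hit is significance in either direction at any visit.

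| Assumed cumulative share (%) | 24.1% | 38% | 52.2% |
|---|---|---|---|
| 20/40/60/80/100 | 7.8% | 11.2% | 13.6% |
| 30/60/75/85/100 | 7.9% | 11.3% | 13.2% |
| 40/80/90/95/100 | 7.6% | 10.1% | 12.4% |
| 60/90/94/97/100 | 7.1% | 9.6% | 11.5% |

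With chi-squared throughout, the range is 10.2% to 16.6%. With a choice only between 6 weeks and 2 years it is 5.5% to 9.1% under the plan's rule. The first pattern puts 60% of events after 6 weeks. Recurrence, at 5-10% in Potential Risks, could supply at most about 10/52.2 = 19% of a 52.2% composite, so that row needs many other late events that the documents do not suggest.

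**4. Planning rates and window.** If the window used captured 90% or 75% of both planning rates (assumed), power at 50 per arm would fall from 83.5% to 76.7% or 64.9% (normal approximation). The documents do not indicate that such a mismatch exists. Nor do they support the idea that robotic recurrences had not yet been counted: the planning composite includes recurrence, and Potential Limitations calls recurrence similar in the two approaches.

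**5. Is one window plainly right?** Counting everything to 2 years loses no event but has costs. With 40 evaluable per arm (an assumed 20% loss) power is 75.0%. If 5%, 10% or 20% of otherwise event-free patients in each arm had an unrelated readmission (assumed), the rates become 54.6/27.9%, 57.0/31.7% or 61.8/39.3%, for example 0.522 + 0.478·0.05 = 0.546. Exact power at 50 per arm is then 79.3%, 74.5% or 64.2%. A shorter window avoids much of this but misses later recurrence.

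**6. Seroma and hematoma.** Data Collection sends all patients to the hernia registry and lists the extra items the registry lacks. Site occurrences, infections and recurrence are not among the extras, so the registry presumably holds them. Whether it defines the two collections cannot be seen from the documents, and the effect of mislabelling cannot be sized.

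**The case for a change.** The strongest case for a change is that nothing in the text says events are counted through 2 years. A primary endpoint should be reproducible from the protocol without guessing, and one sentence would settle it at almost no cost. The false-positive figures are sound as bounds on what the wording permits. The planning rates do lack a follow-up length, and the robotic technique is described as novel, so asking whether both arms were followed equally is fair. The watery/bloody description is lay text and does not classify a collection that nobody has drained.

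All of that stands as a description of what is unwritten. What does not stand is the step from unwritten to unsound. The inflation requires someone to choose the visit by its result, and nothing in the documents points that way. The figures also count significance in either direction. False claims of robotic benefit, the direction of the hypothesis, are about half of them, although a single test halves in the same way. The sample-size section's wording, which excludes seromas without the word simple, can be read as shorthand for the endpoint definition.

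**Conclusion.** The omissions are real but are gaps in documentation. The plan describes one comparison per outcome between arms, no testing by visit, and an enrolment margin for patients not kept in follow-up. The natural reading is one count per patient over the scheduled follow-up, tested once, and that holds the error rate at 4.4% to 5.7%. The 7% to 14% range applies only to a visit chosen after seeing results, under assumed event timing. The sample size is correct for its inputs, and 83.9% power at 50 per arm holds if the planning rates suit the window used. Which window is best is a fair trade-off between completeness, loss to follow-up and dilution by unrelated readmissions, on which statisticians would reasonably differ. The seroma/hematoma gap is confined to undrained collections, may be covered by the registry, and cannot be sized.

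This conclusion assumes that the window, and the handling of patients lost before its end, are settled without reference to results by arm, and that fluid collections are labelled alike in both arms. On that footing no change to the plan follows.

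### The primary composite is compared without adjusting for the four risk factors the protocol itself says raise morbidity, which gives up some precision

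*Combined protocol and SAP*

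**What the plan says.** The Background states: "Obesity, COPD, DM, and tobacco abuse are particularly troublesome conditions that confer higher morbidity after abdominal wall reconstruction (AWR"). The Inclusion Criteria use the same four conditions as the entry requirement, under "At least one of the following risk factors". They are BMI above 30, COPD, diabetes and current smoking, so an enrolled patient carries between one and four.

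Data Collection lists them among the registry items: "Patient characteristics include DM, COPD, HTN, immunosuppression, smoking status, hepatic disease, renal disease". BMI follows later in the same sentence. Since eligibility depends on these factors, they can be known before allocation.

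Methods describes allocation in one sentence, "Randomization will be performed using the randomize function in the Redcap database". It names no stratification factor, block or minimisation.

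Sample Size & Statistical Analysis says the discrete primary and secondary outcomes "will be analyzed using Chi-squared tests, or Fisher's Exact Test for small sample sizes". No adjusted, stratified or sensitivity analysis is planned for any outcome.

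**The concern.** The protocol treats these four factors as important enough to define the population, then ignores them in the comparison. One patient may enter with a single factor and another with all four. If the factors predict the composite, part of the outcome variation within each arm is explainable from data in hand, and an unadjusted test leaves it in the error.

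Two things are at stake. One is some power and a tighter estimate from the same 100 patients. The other is credibility: if a visible imbalance appears in the baseline table, an adjustment chosen after seeing the data will persuade fewer readers than one fixed beforehand.

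**Working it through.** **1. The plan's own figure.** Inputs from Sample Size & Statistical Analysis: composite rates 52.2% (open) and 24.1% (robotic), power 80%, significance 5%, 46 per arm. With a two-sided test, pooled variance under the null and no continuity correction:

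- mean rate = (0.522 + 0.241)/2 = 0.3815
- √(2 × 0.3815 × 0.6185) = 0.6870
- √(0.522 × 0.478 + 0.241 × 0.759) = 0.6576
- n = (1.960 × 0.6870 + 0.8416 × 0.6576)² / 0.281² = 45.7, so 46 per arm

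The stated figure is reproduced. By the same formula, power is 80.3% at 46 per arm and 83.5% at 50.

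**2. How large chance imbalance may be.** If K of 100 patients carry a factor and each arm has 50, the number X in one arm is hypergeometric(100, K, 50), and the gap between arms is |2X − K|/50.

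| Carriers | Gap | Condition | Probability |
|---|---|---|---|
| 30 of 100 | at least 12 points | X ≤ 12 or X ≥ 18 | 27.5% |
| 30 of 100 | at least 20 points | X ≤ 10 or X ≥ 20 | 4.9% |
| 50 of 100 | at least 20 points | X ≤ 20 or X ≥ 30 | 7.1% |

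For at least one of the four factors, taken as independent with assumed prevalences of 80%, 20%, 30% and 30% (two binomials of 50), the probability is 75% for a gap of at least 10 points and 11% for at least 20.

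**3. What such a gap does to the estimate.** Shift ≈ imbalance × risk difference associated with the factor. At an assumed prevalence of 40% and the open-arm rate of 52.2%, an odds ratio of 2 corresponds to 17.1 points and an odds ratio of 3 to 26.5 points.

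- 12-point gap: 0.12 × 17.1 = 2.1 to 0.12 × 26.5 = 3.2 points
- 20-point gap: 0.20 × 17.1 = 3.4 to 0.20 × 26.5 = 5.3 points

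The planned difference is 28.1 points. Its standard error is 0.6576/√50 = 0.093, or 9.3 points, which already includes this source of variation.

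**4. What adjustment gains at 50 per arm, by simulation.** The documents give no prevalences or prognostic strengths, so these are assumptions. The arm-level rates were held at 52.2% and 24.1%.

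| Scenario | Unadjusted power | Adjusted power |
|---|---|---|
| Count of four factors, odds ratio 1 each | 84% | 84% |
| Count of four factors, odds ratio 2 each | 84% | 86% |
| Count of four factors, odds ratio 3 each | 84% | 88% |
| One binary factor (prevalence 40%), odds ratio 2 | 84.1% | 84.5% |
| One binary factor, odds ratio 3 | 83.8% | 85.5% |
| One binary factor, odds ratio 4 | 83.9% | 86.9% |

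The count rows use logistic regression on arm and count, with assumed prevalences of BMI above 30 60%, COPD 15%, diabetes 30% and smoking 25% before requiring at least one factor. An obesity prevalence of 80% gave the same gains of about 2 and 4 points. The single-factor rows use a Cochran-Mantel-Haenszel test. That test cost about half a point when the factor had no effect (83.9% to 83.4%).

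**5. Type I error.** It was near 5% for both approaches. The unadjusted test ran at 5.6% to 5.9%, including when no factor was prognostic, so the small excess comes from the discreteness of the test and not from imbalance.

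**6. What stratified allocation adds once the analysis adjusts** (single-factor model): 84.5% to 84.7% at odds ratio 2, 85.5% to 85.6% at 3, and 86.9% to 87.1% at 4.

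**The case against.** The strongest reply is that nothing here is wrong. Randomisation makes the unadjusted test valid, its p-value already allows for chance imbalance, and at 50 per arm it has more than the 80% power the plan asked for. All of that stands. The gain is modest, and if only one factor matters with an odds ratio of 2 it is under half a point.

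A reader might infer more than the documents support:

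- **That the comparison is biased or its error rate inflated.** It is not, as the type I error results show. A single realised estimate can be off by a few points, which is ordinary sampling variation.
- **That allocation is known to be unstratified.** The protocol is silent: no stratification is specified, and that is all that can be said.
- **That severe imbalance is likely.** A gap of about 10 points in some factor is likely under the assumed prevalences. A gap of 20 points is not.
- **That hernia width is a fifth baseline factor ready to be used.** The Background does not name it among the conditions that raise morbidity after abdominal wall reconstruction. Data Collection lists it under operative details, and Operative Technique measures the defect during surgery, by different means in the two arms. The recorded width therefore arises after randomisation.

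**Conclusion.** The point holds as one of precision and prespecification, not of validity. The plan leaves four recorded factors, which it names itself as raising morbidity, out of the analysis of its primary composite. Using them would be worth about 1 to 4 points of power if each has an odds ratio of 2 to 3, and would cost essentially nothing if none is prognostic. These sizes rest on the assumed prevalences and odds ratios. The sample size of 46 per arm is unaffected.

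The benefit could matter more than these figures suggest if the true difference is smaller than 28.1 points. Potential Limitations describes the current outcome measures other than length of stay as similar between approaches, and a shift of 2 to 5 points would then be a larger share of the effect.

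**What to change.** In Sample Size & Statistical Analysis, prespecify the primary analysis of the composite as a logistic regression on arm and the number of eligibility risk factors present (BMI above 30, COPD, diabetes, current smoker). Report the result as an adjusted risk difference with its confidence interval, averaging predicted risks over all randomised patients. Keep the chi-squared test as the supporting analysis. At the planned rates about 50 × 0.522 + 50 × 0.241 = 38 events are expected, enough for a model with two terms.

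Optionally, stratify the REDCap allocation by the same count (1 versus 2 or more), with concealed and varying block sizes. Concealment matters because this is one centre with allocation in the office and surgeons who know the arm. Stratifying on all four factors separately would leave sparse strata with 100 patients. In either case, state the allocation method.

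Do not use the recorded hernia width as a covariate or stratum. Defect size could serve only if the preoperative measurement that decides eligibility is entered before randomisation.

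The cost is one additional prespecified model on values already collected, and a slightly more complex allocation table if the optional stratification is adopted.
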